Appendix A: Flow diagram illustrating dataset construction, including codes where applicable.

Appendix B: Registries, codes, and variables for each outcome

Outcome	Registry	Codes for Registry
Primary Outcome: Prosthetic Joint infection	Danish Hip Arthroplasty Registry (DHR) The Hospital Acquired Infections Database (HAIBA) The Danish Microbiological Database (MiBa)	Code for revision for infection in DHR: DHR: Variable 2: "Revision" HAIBA: Variable "SSI_acute_90 = 0 OR 1", 0 = infection that occurred between 3 and 90 days after a planned index operation. 1 = infection that occurred between 3 and 90 days after an acute index operation. MiBA: "Prøvedato"=corresponding to date or revision, "Resultat"=positive for microorganism, "Prøvemateriale"=closed fluid aspirate taken intraoperatively, "Konklusion på undersøgelse" or "Dyrkningsfund" = phenotypically indistinguishable from bacteria found in tissue biopsy
Serious Adverse Events	The Danish National Patient Registry (DNPR) The Civil Registration System	Please see Appendix XX for the complete outline of ICD-10 codes. The civilregistration system: variable: date of death
PJI-likely	The Danish Microbiological	MiBA: "Prøvedato"= between 3 and 90 days after a planned index operation , "Resultat"=positive for microorganism, "Prøvemateriale"=aspiration of synovial fluid OR closed fluid aspirate taken

	Database (MiBa) The Danish National Prescription Registry (NPR)	intraoperatively, "Lokation" = corresponding to THA from index surgery "Undersøgelse" = aspiration with or without imaging guidance or biopsy "Konklusion på undersøgelse" or "Dyrkningsfund" = phenotypically indistinguishable from bacteria found in tissue biopsy From the prescription database (NPR): (ATC category J01
Length of stay for hospitalization	The Danish National Patient Registry (DNPR)	From date of index surgery to date of discharge.
Major Adverse Cardiovascular Events	The Danish National Patient Registry (DNPR)	The following ICD.10 codes: Venous thromboembolism: I26, I80.1 –I80.9, I82 or T81.7 Myocardial infarction: I20 – I25 Atrial fibrillation: I48.0 -I48.92 Stroke: I60.0 - I64.0
Hospital-treated infections (Other than PJI and PJI-likely)	The Danish National Patient Registry (DNPR)	A20 -A38, A42 -A44, A48 -A49, A65 -A79, A3, A49.9, A39.4, A40 -A41, B37.7, A32.7, A54.8G, A02.1, A22.7, A26.7, A42.7, A28.2B, A06.5, A54.1, B43, D73.3, E06.0A, E23.6A, E32.1, G06, G07, H00.0A, H05.0A, H44.0A,

	
H60.0, J34.0A, J36, J38.3D, J38.7G, J39.0, J39.1, J39.8A, J85.1, J85.2, J85.3, K04.6, K04.7, K11.3, K12.2, K13.0A, K14.0A, K20.9A, K35.3A, K35.3B, K57.0, K57.2, K57.4, K57.8, K61, K63.0, K65.0, K75.0, K81.0A, K85.8A, L02, L05.0, L05.9, M60.8A, M86.8A, M86.9A, N15.1, N34.0, N41.2, N45.0, N48.2, N49.2A, N61.9A, N61.9B, N70.0A, N70.0B, N71.0A, N73.0A, N73.0B, N73.2A, N73.2B, N73.3A, N73.5A, N73.8A, N73.8C, N75.1, N76.4, N76.8A, Except: A54.1B, B43.0, B43.8, B43.9, K57.0B, K57.0C, K57.2B, K57.2C, K57.4A, K65.0M, K65.0N, K65.0O, K65.0P, A46, H01.0, H03, H60.0, H60.1, H60.2, H60.3, H62, K12.2, K13.0, K61, M72.6, L01, L08, L03, J34.0, L00, L02, L04, L05, L06, L07, L30.3, L73.8, H00, H01.0, H03.0, H03.1, H04.3, H05.0, H06.1, H10, H13.0, H13.1, H15.0, H19.1, H19.2, H22.0, H32.0, H44.0, H44.1, H60, H61.0, H62.0, H62.1, H62.2, H62.3, H65, H66, H67.0, H67.1, H68, H70, H73.0, H75.0, H83.0, H94.0 Except: H60.4, H60.4A, H605, H60.5B, H60.8, H608.A, H65.2, H65.3, H65.4, H65.4C, H66.1, H66.2, H66.3, H68.1, H70.1, H70.8, G00 -07, A80 - A89, G00, G01, G02, G03, A32.1, A39.0, A17.0, A20.3, A87, A54.8D, A02.2C, B37.5, B00.3, B01.0, B02.1, B05.1, B26.1, B38.4, A00 -A09, K35, K37, K57.0, K57.2, K57.4, K57.8, K61, K63.0, K65.0, K65.9, K67, K75.0, K75.1, K80.0, K80.3, K80.4, K81.0, K81.9, K83.0, K85.9, I00 -I02,

--	--

		
I30.1, I32.0, I33, I38, I40.0, I39.8, B37.6, J00 - J06, J36, J39.0, J39.1, J12 -J18, J20 - J22, J44.0, J85.1, J86, J20 -J22, J34.0, J35.0, J38.3C, J38.3D, J38.7B, J38.7F, J38.7G, Except: J34.0E, J34.0F, J34.0G, J34.0H, N10, N11, N12, N15.1, N15.9, N30, N33.0, N34, N39.0, N08.0, N13.6, N16.0, N28.8D, N28.8E, N28.8F, N29.0, N29.1, Except: N30.1, N30.2, N30.4, A50 -A64, N41, N45, N48.1, N48.2, N49, N51.1, N51.2, N70 -77, O23, O26.4, O41.1, O74.0, O75.3, O85, O86, 088.3, O91, O98, M00, M01, M86, M63.0, M63.2, T80.2, T81.4, T82.6, T82.7, T83.5, T83.6, T84.5, T84.6, T84.7, T85.7, T88.0, T89.9, B90 -B99, K04.0, K05.2
 
Codes for specific Hospital-treated infections
 
Pneumonia: J12-J18
 
Urinary tract infections N10, N11, N12, N15.1, N15.9, N30, N33.0, N34, N39.0, N08.0, N13.6, N16.0, N28.8D, N28.8E, N28.8F, N29.0, N29.1, Except: N30.1, N30.2, N30.4

Community-based antibiotic use	The Danish National Prescription Registry (NPR)	
Narrow spectrum antibiotics: J01CE, J01CF, J01DB
 
Broad spectrum antibiotics: J01DC, J01DD, J01DE, J01DH, J01DI, J01CR, J01CA, J01F, J01E, J01MA, J01AA

Opioid use	The Danish National Prescription Registry (NPR)	Following ATC codes (including all subcodes) are included: N01AH (opioid anesthetics), N02A (opioids), N07BC02 (methadone), and R05DA04 (codeine).
Use of acetaminophen or non-steroidal anti-inflammatory drugs	The Danish National Prescription Registry (NPR)	Acetaminophen ATC codes: N02BE01 and N02BE51 Non-steroidal anti-inflammatory drug ATC codes: M01A
Any revision after THA	Danish Hip Arthroplasty Registry (DHR) and The Danish National Patient Registry (DNPR)	Code for revision for infection in DHR: DHR: Variable 2: "Revision"

Appendix C: International Classification of Diseases, 10th Revision Diagnosis Codes for Serious Adverse Events

Serious Adverse Event	ICD-10 Diagnostic Code
Sepsis	A40 - A41
Shock not elsewhere classifies R67	R67
Anaphylactic Shock, unspecified	T78.2

Other types of shock included in codes below	
 • anesthesia (T88.2) • anaphylactic (due to): 
 ◦ serum (T80.5) • postoperative (T81.1) • traumatic (T79.4)
Staphylococcal scalded skin syndrome	L00
Infectious arthropathies	M00-M03
Osteomyelitis	M86
Injuries to the hip and thigh	S70-S79
Poisoning by drugs, medicaments and biological substances	T36 – T50
Certain early complications of trauma, not elsewhere classified	T79
Complications of surgical and medical care, not elsewhere classified	T80 – T88
Pneumothorax	J93
Respiratory failure, not elsewhere classified	J96
Postprocedural respiratory disorders, not elsewhere classified	J95
Adult respiratory distress syndrome	J80
Pulmonary oedema	J81
Cardiac arrest	I46

Other forms of heart disease	I30 – I52
Ischemic heart diseases	I20 – I25
Acute and subacute endocarditis	I33
Acute myocarditis	I40
Heart failure	I50
Complications and ill-defined descriptions of heart disease	I51
Pulmonary heart disease and diseases of pulmonary circulation	I26-I28
Arterial embolism and thrombosis	I74
Phlebitis and thrombophlebitis	I80
Portal vein thrombosis	I81
Other venous embolism and thrombosis	I82
Intracranial and intraspinal phlebitis and thrombophlebitis	G08
Postprocedural disorder of circulatory system, unspecified	I97.9
Acute kidney failure	N17
Type 1 diabetes mellitus with diabetic ketoacidosis	E10.1

Type 2 diabetes mellitus with diabetic ketoacidosis	E11.1
Other specified diabetes mellitus with diabetic ketoacidosis	E13.1
Stroke	I60-I64
External causes of morbidity and mortality	Y40 – Y84
Acute appendicitis	K35
Acute peritonitis	K65
Perforation of intestine	K63.1
Abscess (perianal, ischiorectal, intraspincteric)	K61
Hemoperitoneum	K66.1
Other and unspecified intestinal obstruction	K56.6
Ileus	K56
Hematemesis	K92.0
Melena	92.1
Gastrointestinal hemorrhage unspecified	92.2
Acute Pancreatitis	K85
Cholangitis	83.0
Acute cholecystitis	K81.0
Perforation of gallbladder	K82.2
Abscess of liver	K75.0

Perforation of the esophagus	K22.3
Gastric ulcers with bleeding or perforation	K25.0 to K25.6
Duodenal ulcers with bleeding or perforation	K26.0 to K26.6
Gastrojejunal ulcers with bleeding or perforation	K28.0 to K28.6
Diverticular disease with perforation, abscess, or bleeding	K57.0, K57.2, K 57.4, K57.8
Diaphragmatic hernia with obstruction or gangrene	K44.0, K44.1
Peritonitis	K65
Abscess of intestine	K63.0
Perforation of intestine	K63.1 (non traumatic)

Serious Adverse Event	ICD-10 Diagnostic Code
Surgical site infection	T81.40, T81.41, T81.42, T81.43, T81.49
Venous thromboembolism	I26, I80, T81.7B
Cardiac Arrest	I46, I97.12
Acute myocardial Infarction	I21
Stroke	I60 - I64
Pancreatitis	K85

Pneumonia	J13, J14, J15, J16, J17, J18, J85.1, T81-4P
Acute kidney injury	N17
Wound dehiscence	T81.3

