variations, both measures will be averaged over the 5 years preceding the primary THA. Family income and liquid assets will be each categorized into tertiles (low, medium, and high) for their age and combined into a single wealth variable. Numbers and percentages will be calculated and presented for categorical variables. Means and SD will be computed and presented for continuous variables if data follows a normal distribution. In case continuous variables are not normally distributed, median and interquartile range will be calculated. No tests of statistical significance will be conducted for any baseline characteristic variable. However, imbalances with clinical importance will be noted. The baseline characteristics will be presented as illustrated in Mock-up **Table 1**.

ANALYSIS

A flow diagram illustrating dataset construction, including codes where applicable (Appendix A). Every outcome was defined according to specific codes in well-defined registries and databases (Table Appendix B).

Interventions

Patients will have received either one single dose of preoperative antibiotic (i.e. single dose) or one preoperative antibiotic dose followed by three postoperative dosages administered within the first 24 hours after index surgery (i.e. multiple dose) .The dosages and antibiotic agents applied have also been outlined in the protocol article (32) as well as the registration on ClinicalTrials.gov, registration ID NCT05530551 and are the following:

Antibiotic Practice Treatment A and B

		Single-Dose (A) / Multiple-Dose (B)	Multiple-Dose(B)		
Antibiotic	Weight	Preoperative dose	6 hours postoperative	12 hours postoperative	18 hours postoperative
Cloxacillin i.v.	< 120 kg	2 g	1 g	1 g	1 g
	> 120 kg	3 g	2 g	2 g	2 g
Cefuroxime i.v.	< 120 kg	1.5 g	750 mg	750 mg	750 mg
	> 120 kg	3 g	1.5 g	1.5 g	1.5 g

Possible transition to oral postoperative antibiotic treatment.

The first postoperative dose of cloxacillin or cefuroxime must be administered intravenously.

Antibiotic	12 hours postoperative	18 hours postoperative
Dicloxacillin oral	1 g	1 g
Amoxicillin and clavulanic acid oral	875 mg/125 mg*	875 mg/125 mg*

No weight adjustment.

*If the center or region does not have access to amoxicillin and clavulanic acid 875/125 mg, a dose of 1 g / 125 mg (i.e. amoxicillin 500 mg + amoxicillin and clavulanic acid 500 mg/125 mg) may be used.

Antibiotic Practice in cases of cephalosporin allergy or general beta lactam allergy

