The definition has been simplified to allow for the capture of PJI through databases and registries without review of medical files and the modifications are expected only to give minor non-significant changes for the capture of PJI (34, 36). Data will be extracted from DNRP, DHR, MiBA and HAIBA. Positive culture samples (aspirations, tissue biopsies or fluid) must be obtained from the relevant hip joint. As part of standard care, a sample of at least 5 tissue biopsies are obtained at revision surgery. All samples are sent for microbiological analysis at one of ten regional departments of clinical microbiology who have standardized methods for handling of biopsies and culturing. The cumulative proportion of patients remaining PJI-free in the two groups will be presented as illustrated in Mockup Figure 2.

Key secondary endpoints evaluated within 90 days from primary THA

1) Serious Adverse Events (SAEs)

Number of patients with one or more SAEs. SAEs are defined according to the guidelines provided by the International Council for Harmonization of Technical Requirements for Human Use (ICH-GCP) (39). SAE refers to an event involving a significant risk of death or disability of the patient (or their offspring), including, but not limited to, an event that: (1) results in death, (2) is life-threatening – in the investigator's opinion the patient was in immediate risk of death from the adverse event when it appeared, (3) requires hospitalization or prolongs existing hospitalization (4) results in permanent or significant disability. SAEs are recorded from DNPR. The list of ICD10 codes to identify SAEs is listed in Appendix C. This list has been curated to include diagnoses that are considered clinically significant, potentially life-threatening, requiring hospitalization, or resulting in persistent or significant disability/incapacity. To ensure comprehensive coverage and adherence to international standards, any additional codes that meet the criteria for SAEs as defined by the ICH-GCP guidelines will also be included.

2) Potential PJI referred to as *PJI-likely*

Incidence of potential PJI. PJI-likely is defined as at least one of the two criteria is fulfilled:

A: One single intraoperatively obtained positive culture obtained from reoperation (aspiration fluid OR tissue biopsy) regardless of microorganism

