B: One single positive culture obtained from aspiration of synovial fluid regardless of microorganism AND any antibiotic prescriptions (ATC category J01) redeemed

These definitions of PJI-likely are based on a modified version of EBJIS (33) as described previously (see primary outcome) and the study by Milandt *et al.* (40) where first-time revisions with one positive culture were found to have a higher risk of re-revision for PJI.

Cases of PJI-likely, will be captured in HAIBA and MIBA, and registration of antibiotic prescription in NPR. Positive culture samples (aspirations, tissue biopsies or fluid) must be obtained from the relevant hip joint.

3) Length of stay for hospitalization (LOS)

Length of hospital stay (continuous measure [days]) is defined as number of postoperative overnight stays, including transfers to other departments and hospitals within 24 hours. Data on LOS is acquired from DNPR.

4) Major Adverse Cardiovascular Events

Incidence of Major Adverse Cardiovascular Events (MACE). A MACE is defined a priori to include thromboembolic complications including venous thromboembolism, myocardial infarction, atrial fibrillation and stroke based on the diagnostic ICD10 codes listed in Appendix B. VTE is defined a priori as both deep venous thromboembolisms confirmed by compression ultrasound and pulmonary embolism confirmed by spiral computed tomography (CT), ventilation-perfusion scintigraphy or pathological removal of an embolus and based on the following diagnostic ICD10 codes: I26, I80.1-I80.9, I82.1-I82.9, or T81.7B-D. Data will be extracted from DNPR.

5) Hospital-treated infections (Other than those listed above)

Patients with at least one hospital-treated infection are defined as those with first-time hospital admission for a primary or secondary infection diagnosis following discharge from the index THA surgery. Hospital-treated infections are identified from DNPR based on ICD-10 codes listed in Appendix B. The list of infections includes chronic and more rare infections, to detect possible flare-ups in any possible ongoing infections. This outcome does not include infections treated during index admission for arthroplasty surgery.

6) Community-based antibiotic use

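### Appendix B, which the SAP makes the outcome definitions, does not match the SAP's own text for PJI-likely and MACE and leaves the exclusion for hospital-treated infections unclear

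*SAP*

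**What the plan says.** The opening of the SAP's Analysis section gives Appendix B its authority: "Every outcome was defined according to specific codes in well-defined registries and databases (Table Appendix B").

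**PJI-likely.** Item 2 of the key secondary endpoints requires at least one of two criteria. Criterion A is "One single intraoperatively obtained positive culture obtained from reoperation (aspiration fluid OR tissue biopsy) regardless of microorganism". Criterion B is "One single positive culture obtained from aspiration of synovial fluid regardless of microorganism AND any antibiotic prescriptions (ATC category J01) redeemed". The section heading sets the window: "Key secondary endpoints evaluated within 90 days from primary THA". On sources, the text says that cases "will be captured in HAIBA and MIBA, and registration of antibiotic prescription in NPR".

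The Appendix B row gives the sample material as "aspiration of synovial fluid OR closed fluid aspirate taken" intraoperatively. It gives the sample date as "between 3 and 90 days after a planned index operation", names aspiration or biopsy as the examination, and requires the culture finding to be "phenotypically indistinguishable from bacteria found in tissue biopsy From the prescription database (NPR"). It names MiBa and NPR as sources, but not HAIBA.

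**MACE.** Item 4 refers to Appendix B for codes but also writes out a VTE list of its own: I26, I80.1-I80.9, I82.1-I82.9 and T81.7B-D. Appendix B has I26, I80.1-I80.9, I82 and T81.7. Appendix B codes the myocardial infarction component as I20-I25. Appendix C labels that same range ischemic heart diseases and gives I21 for acute infarction.

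**Hospital-treated infections.** The section on timing of secondary outcome assessments and the Appendix B row label both exclude PJI and PJI-likely. The Table 2 label excludes SSI. The Appendix B code list contains T81.4, and Appendix C lists subcodes of T81.4 under surgical site infection.

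**The concern.** These endpoints are built by a programmer from registry fields and codes. No case review stands between the code list and the result, so an error in the list becomes an error in the endpoint. Where text and appendix disagree, two programmers who each follow the SAP faithfully can extract different endpoints, and the SAP does not say which source governs.

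The PJI-likely row matters most. The endpoint exists to catch infections that fall short of the full PJI definition because only one culture is positive. A row that asks for agreement between fluid and tissue moves towards the primary definition and away from that purpose. For MACE, the risk is a composite broader than its named components. For hospital-treated infections, it is an unstated choice about whether surgical site infection counts.

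**Working it through.** No formula applies. The check sets each row against the text, Table 2 and Appendix C.

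**1. PJI-likely.** The match condition also stands in the primary PJI row, where it corresponds to primary criterion 2 (fluid and tissue with indistinguishable bacteria). The row does not say how its fields combine. The table takes the microbiology fields as joint conditions and leaves the prescription field aside.

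| Case | Text | Row, fields joint |
|---|---|---|
| One positive intraoperative tissue culture only | meets A | fails: tissue is not a listed material |
| One positive intraoperative fluid culture only | meets A | fails: no tissue match |
| Positive synovial aspirate, J01 redeemed, no biopsy | meets B | fails: no tissue match |
| Intraoperative closed fluid matched to tissue | already meets primary criterion 2 | passes |

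Under that reading, the row drops the three single-culture cases and keeps one that is already PJI. If the fields are instead a list of variables to consult, the second and third cases could be kept. The first would then depend on whether biopsy as an examination type is enough when the material field lists two fluids and no tissue. Under neither reading is a tissue match part of criterion A or B.

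Window: the row covers days 3 to 90 and the text covers everything within 90 days, so a sample taken before day 3 counts under the text and not under the row.

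**2. MACE.**
- VTE: I82 less I82.1-I82.9 leaves I82.0. T81.7 less T81.7B-D leaves the other T81.7 subcodes. I26 and I80.1-I80.9 agree. Appendix B is therefore a strict superset of the text.
- Infarction: I20, I21, I22, I23, I24 and I25 are 6 categories. Appendix C's acute infarction code is I21, which is 1. 6 − 1 = 5 categories lie outside that code.
- Table 2 has one MACE line, so both differences widen the composite.

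**3. Hospital-treated infections.**
- Exclusion in the timing section and the Appendix B label: PJI and PJI-likely.
- Exclusion in Table 2: SSI.
- T81.4 is in the code list and in none of its exception lists. Appendix C places T81.40, T81.41, T81.42, T81.43 and T81.49 (5 subcodes) under surgical site infection.
- If SSI in Table 2 has its Appendix C meaning, the list contradicts the table. If it is shorthand for PJI, the labels agree in intent and only the wording is loose.

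**Count.** Two of the 9 key secondary endpoints conflict with the SAP's own text or labels (PJI-likely, MACE), and one is unclear (hospital-treated infections). Three further differences are editorial: HAIBA is absent from the PJI-likely row; N02BE51 is in the Appendix B acetaminophen codes but not in the text; and the any-revision row carries a heading about revision for infection.

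**The case against.** The strongest defence is that Appendix B is a list of fields, not a set of joint rules. Requiring every PJI-likely entry at once would also impose a J01 redemption on criterion A, which the text does not do. Likewise, the MiBa fields in the primary row describe only one of three criteria that the text joins by and/or. This stands as a limit. A reader might infer that the single-culture cases will be lost. The SAP does not establish that, because it leaves the combination unstated and names biopsy as an examination type. The defence does not rescue the match condition, which belongs to neither criterion under any combination.

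On MACE, a reader might infer that other ischemic heart disease will be reported as myocardial infarction. The tables do not support this. Table 2 shows only the composite, and the acute infarction line in Table 3 is a serious adverse event, for which Appendix C gives I21. The text also refers to Appendix B for the infarction codes, so there is no second MACE code set. The fault is a label that its codes exceed.

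On infections, SSI in Table 2 may well mean PJI, since the HAIBA variable used for the primary outcome is itself named SSI_acute_90. A proven contradiction over T81.4 is therefore not shown. Nor can it be said that the SAP lacks a step removing PJI and PJI-likely patients: Appendix A is the dataset construction diagram, and it is not visible in the text at hand.

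Finally, the day 3 to 90 window also stands in the HAIBA variable of the primary row, so it is not peculiar to PJI-likely. It still differs from the endpoint text.

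**Conclusion.** The point holds in this form: Appendix B conflicts with the SAP's own text or labels for PJI-likely and MACE, and the exclusion for hospital-treated infections needs clarifying. It should be corrected. Confidence is medium, mainly because the PJI-likely row does not state its logic. The loss of single-culture cases is conditional on the fields being applied jointly. The unsupported match condition, the wider VTE set and the infarction label are not conditional.

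The number of events affected cannot be derived from the SAP. A reader might infer that the primary non-inferiority conclusion or the comparison between arms is biased. The documents do not support that: only key secondary endpoints are shown to be affected, the SAP already says that these will be interpreted with caution, and the same codes apply to both arms. What is lost is a single prespecified definition for each endpoint.

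**What to change.** Make these edits before the randomization code is unsealed, so that no definition is chosen with results by arm in view.

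- **PJI-likely row:** delete the tissue-match condition, add tissue as sample material, write criteria A and B as two separate rules, and use one time window in text and row.
- **MACE:** use one VTE code set in the text and Appendix B. Either restrict the infarction codes to infarction or rename the component ischemic heart disease.
- **Hospital-treated infections:** the sponsor states one exclusion in identical words in the text, Table 2 and Appendix B, makes T81.4 consistent with it, and confirms that the dataset construction applies it.
- **Editorial:** align the HAIBA source and the N02BE51 code between text and appendix, and correct the heading in the any-revision row.

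The cost is an edit to code lists and labels. The registries are already named as sources, so no new data collection is needed.

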The time point of the assessment of the primary and secondary outcomes is within 90 days after index surgery: SAES, PJI-likely, LOS, MACE, Hospital-treated infections (other than PJI and PJI-likely), Community-based antibiotic use, use of acetaminophen or non-steroidal anti-inflammatory drugs, and any revision after THA. The outcome of opioid use will be evaluated within 6 months before index surgery and within 90 days after index surgery.

STATISTICAL PRINCIPLES

Adherence and protocol deviations

This is a pragmatic randomized trial, applying the intention-to-treat (ITT) principle. The main analysis uses the treatment policy estimand, which quantifies the average treatment effect among all the centers who had undergone randomization, regardless of adherence to treatment or crossover (i.e., the intention-to-treat population). The ITT approach ensures that the results reflect real-world clinical practice, accounting for adherence variations and any protocol deviations (22). Deviations from the protocol and adherence will be monitored and documented during data management, but they will not exclude participants from the primary analysis.

Analysis populations

The primary analyses will be based on the ITT population based on the Full Analysis Set; i.e., all patient's undergoing the prespecified surgery using the antibiotic dose corresponding to the specific cluster and year (cross-over, cluster randomization) (22). Accordingly, participants allocated to a treatment group ($X_{\text{Single-dose}}$ and $X_{\text{Multiple-dose}}$, respectively) will be followed up, assessed, and analyzed as members of that cluster, irrespective of the actual antibiotic regimen used in the specific clinic (i.e., independent of physicians' withdrawals and cross-over phenomena) (23, 24).

TRIAL POPULATION

Screening data

The total number of patients enrolled during the trial period of 2 years, will be collected and reported according to CONSORT flowchart (see **Figure 1**, Mockup below). Furthermore, the

number of ineligible patients including reason for ineligibility and patients with loss to follow-up will be reported.

Eligibility

All patients \geq 18 years receiving a primary THA conforming to the following inclusion and exclusion criteria are considered eligible for the trial.

Inclusion Criteria:

1. primary and secondary causes of osteoarthritis

Exclusion Criteria:

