Comorbidity status will be evaluated using the Charlson Comorbidity index Score (CCI) (26). Information about comorbidities will be collected from DNPR (27, 28) after linkage using CRS(29) (27). The CCI score will be calculated based on all primary and secondary diagnoses from hospitalizations and outpatient visits registered as ICD-10 codes in the DNPR over a 10-year period before the primary THA. Although the positive predictive value (PPV) for diagnosis and treatment varies substantially in the DNPR (27), the overall PPV for the 19 Charlson conditions has been found to be 98.0% (30). For each patient that undergoes surgery during the trial period, information on SES will be based on retrieved information on marital status, cohabitation, highest obtained level of education, occupation, family income, and a measure of family liquid assets on the index date retrieved from Statistics Denmark (31). SES will be categorized into the following three domains: educational level, income, and employment status. Educational level will be categorized as low, medium, or high. Low includes no education or high school completed, medium includes vocational education or higher preparatory programs, and high includes a bachelor's or higher degree. Cohabitation status will be classified as living alone, cohabiting, or other. Cohabitation status will be classified as living alone or cohabiting with an adult partner (married, unmarried, or living in multifamily housing). Wealth will be determined using either family income (total in a co-housing family before taxes) or family liquid assets (including cash property value, bank deposits, and securities such as stocks, bonds, and mortgage deeds), depending on the patient's age. For patients aged ≥ 65 years, the standard retirement age in Denmark, family liquid assets will be used, as income may no longer accurately reflect financial status. For patients aged < 65 years, family income will be used. Family income at the time of THA is calculated as the average annual pre-tax income in kroner (1 Euro \approx 7.5 Kroner) over the 5 years prior to surgery. Income is classified as above or below the mean for each age group (0-59, 60-69, 70-79, 80+). To account for annual

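### The MACE definition counts any atrial fibrillation code within 90 days, so long-standing atrial fibrillation is scored as an incident complication

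*SAP*

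**What the plan says.** The fourth key secondary endpoint in the SAP is introduced as "Incidence of Major Adverse Cardiovascular Events (MACE"), and its components are described as complications. They include "myocardial infarction, atrial fibrillation and stroke based on the diagnostic ICD10 codes listed in Appendix B", with data taken from DNPR. The Analysis section gives the code table its authority: "Every outcome was defined according to specific codes in well-defined registries and databases". In the MACE row of Appendix B the whole entry for this component is "Atrial fibrillation: I48.0 -I48.92". The section on timing of secondary outcome assessments adds the window: "The time point of the assessment of the primary and secondary outcomes is within 90 days after index surgery".

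The visible text says nothing more about which atrial fibrillation codes qualify. It does not ask for a first diagnosis, exclude patients coded before surgery, restrict the type of diagnosis or contact, or say whether codes from the index stay count.

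Other registry outcomes in the same SAP do have such rules. Hospital-treated infection is a "first-time hospital admission for a primary or secondary infection diagnosis following discharge from the index THA surgery", and infections treated during the index admission are excluded. Opioid use separates prior users from naïve patients by a six-month look-back. For the Charlson index the SAP already draws on diagnoses "registered as ICD-10 codes in the DNPR over a 10-year period before the primary THA".

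**The concern.** An outcome called an incidence of complications should count events that arise after surgery. Atrial fibrillation is often a long-standing condition, and a registry code for it can simply record that the patient has it. Under the written definition, a patient with years of known atrial fibrillation becomes a MACE case if the code is entered as a comorbidity at the index stay or at a routine visit within 90 days.

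Disease that was present before surgery cannot depend on the number of antibiotic doses. Counting it adds about the same number of non-events to both groups. For a harm outcome reported as an odds ratio, that shrinks the apparent relative effect, adds noise, and makes the reported MACE percentage higher than the complication rate it is meant to describe.

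**Working it through.** **Figures in the plan.** The SAP states no MACE rate, effect size or power, so there is no figure to reproduce. What follows is an illustration.

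**Inputs.**
- Group size *n* = 10,000 (SAP, sample size section: up to 10,000 per group).
- Two-sided 5% level (SAP, confidence intervals and p-values).
- True risk of a new MACE with multiple dose, *p*₀ = 2%, varied to 1.5% and 3%: assumption.
- True odds ratio 1.3: assumption.
- Share *q* of patients with long-standing atrial fibrillation coded within 90 days, equal in both groups, 0 to 8%: assumption.
- Clustering ignored.

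**Formulas.**
- *p*₁ follows from the odds: 1.3 × 0.02/0.98 = 0.02653, so *p*₁ = 0.02653/1.02653 = 2.584%.
- Observed risk in each group: *e* = *q* + (1 − *q*)*p*.
- Standard error of the log odds ratio: √[1/(*n e*₀(1−*e*₀)) + 1/(*n e*₁(1−*e*₁))].
- Power ≈ Φ(ln OR / SE − 1.96).
- Half-width of the 95% interval for the risk difference: 1.96 × √[*e*₀(1−*e*₀)/*n* + *e*₁(1−*e*₁)/*n*].

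**Worked case, *q* = 1%.** *e*₀ = 0.01 + 0.99 × 0.02 = 2.98%. *e*₁ = 0.01 + 0.99 × 0.02584 = 3.56%. The odds ratio is 1.201 and the SE is 0.0798. ln(1.201)/0.0798 = 2.30, so power = Φ(0.34) = 63%.

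**Results for *p*₀ = 2%.**

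| *q* | Observed risks, multiple / single | OR | Power | Prevalent share of multiple-dose events | Risk difference ± half-width (points) |
|---|---|---|---|---|---|
| 0 | 2.00% / 2.58% | 1.300 | 79% | 0% | 0.58 ± 0.415 |
| 1% | 2.98% / 3.56% | 1.201 | 63% | 34% | 0.58 ± 0.493 |
| 2% | 3.96% / 4.53% | 1.152 | 52% | 51% | 0.57 ± 0.559 |
| 5% | 6.90% / 7.46% | 1.087 | 33% | 72% | 0.56 ± 0.715 |
| 8% | 9.84% / 10.38% | 1.061 | 24% | 81% | 0.54 ± 0.836 |

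**Other true risks.** At *p*₀ = 1.5%, power is 67% with *q* = 0, 48% with 1% and 22% with 5% (OR 1.07). At *p*₀ = 3%, the corresponding figures are 92%, 84% and 56% (OR 1.12). At *p*₀ = 2%, even *q* = 0.5% gives an OR of 1.241 and power of 70%.

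The direction is the same throughout. The odds ratio falls towards 1, the risk difference hardly moves, and its interval widens.

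**The case against.** The strongest reply is that the wording already points to new events: long-standing atrial fibrillation is neither incident nor a complication, and a sensible analyst would not count it. That shows the intent but does not supply a rule. The operative definition is the code list, and following it literally counts such patients. The content of the Appendix A flow diagram is not shown, so the gap is established for the visible text only.

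Several further points stand and limit the concern:

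- **Size.** Every rate in the illustration is assumed. Long-standing disease counts only if it is actually coded at a DNPR contact in the window. The SAP claims no power for MACE, so the power figures show a loss of information, not a missed target.
- **Absolute scale.** Table 2 reports a risk difference beside each odds ratio. At 5% prevalent coding it moves only from 0.58 to 0.56 points, although less precisely.
- **Components.** Table 3 already lists pulmonary embolism, deep venous thrombosis, acute myocardial infarction and stroke by group, so part of the picture without atrial fibrillation is visible.
- **First-ever diagnosis is not the only defensible rule.** Excluding anyone with an earlier code discards genuine postoperative recurrences of paroxysmal disease. For infections, the SAP deliberately keeps chronic diagnoses in order to detect flare-ups.

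A reader might also infer that comorbidity coding shifts between a centre's two years and so biases the comparison. The document gives no support for this. It expects a stable setting, each centre serves as its own control, and the model includes a period effect.

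**Conclusion.** The definition should be tightened. As written, any I48.0–I48.92 code in DNPR within 90 days is a MACE, so prevalent atrial fibrillation is counted as an incident complication. If it is coded about equally in both groups, the consequences are an odds ratio nearer 1, a less precise risk difference and an inflated MACE percentage. Under the stated assumptions the loss ranges from modest (1% coded: OR 1.20, power 63%) to large (5% coded: OR 1.09, power 33%), against 1.30 and 79% without such coding. The true size cannot be derived from the SAP.

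Two stronger conclusions are not supported. First, the trial's main conclusion is not at risk: the 1.4 margin applies only to prosthetic joint infection, and MACE is one of nine key secondary outcomes that the SAP says it will interpret with caution. Second, it is too strong to say that the plan produces false reassurance about cardiovascular harm, because the absolute difference is reported and nearly preserved, and nothing indicates that one group would be favoured beyond dilution.

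**What to change.** In the MACE endpoint text and the MACE row of Appendix B, count atrial fibrillation only when the first I48 code in DNPR is dated after index surgery and within 90 days, with no I48 code in the 10 years before surgery. State how codes registered at the index stay are treated under this rule. Patients with earlier atrial fibrillation stay in the analysis and can still have a MACE through the other components.

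Add two supporting rows:
- MACE without atrial fibrillation.
- MACE that also counts, in patients with earlier disease, an acute admission after discharge with I48 as the primary diagnosis.

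**Cost.** A sentence or two and a filter on registry data already planned for the Charlson index. There will be fewer MACE events. Recurrences of known paroxysmal atrial fibrillation leave the main count and appear only in the second supporting row. Earlier atrial fibrillation never coded in hospital would still be misclassified.

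**Separate correction needed.** The same row has "Myocardial infarction: I20 – I25", a range that Appendix C labels as ischaemic heart disease, with acute myocardial infarction listed as I21. Established disease enters by that route too. The atrial fibrillation rule alone therefore does not make MACE a count of new events, and the undiluted figures above should not be expected from it alone.
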